 Novo Nordisk

Table 2–2 Flow chart explanatory descriptions

Footer	Description
1	V0 and V1 can be combined to one visit, if the patient fulfils the in- and exclusion criteria
2	When the patient has commenced prophylaxis, visits can for practical purposes be planned according to the predicted number of EDs based on the patient's prophylaxis regimen. A visit does not need to be re-scheduled even if the actual EDs between visits turn out higher or lower due to treatment of bleeding episodes during the home treatment period.
3	If not already on prophylaxis, all patients must initiate prophylaxis treatment no later than at V6. Pre-prophylaxis is only allowed for children below the age of 24 months or up to V6, whatever comes first. Visits at 10EDs±2EDs, 15EDs±2EDs, 20EDs±2EDs must be performed even the window allows 2 visits to be 2 EDs aside (eg ED12 and ED13)
4	Any patient above the age of 3 years should sign a child assent form, if capable, and if required by local requirements. This can be performed on a separate day. As this is a long term trial the investigator should check the progressing maturation of the child and his ability to assent throughout the trial.
5	After Informed consent has been obtained all Adverse Events must reported in the eCRF
6	The frequency of body weight measurements should follow local practice, but should at least be measured every 10 weeks in children ≥ 3 years of age and within a timeframe of 6 weeks in children ≤ 3 years of age. Please refer to Section $8.3.1$
7	Vital signs should be measured prior to dosing at all screening, V1, V9, V14 and EOT. In addition vital signs should also be measured 30±10minutes after the first injection with N8-GP at V1.
8	FVIII activity should only be measured at V0 if diagnosis of haemophilia A (FVIII<1%) has not been documented in the patients' medical record. FVIII activity at V0 can either be measured at local or central laboratory depending on the urgency of receiving the result i.e. in case V0 and V1 are combined
9	Blood samples must be collected prior to dosing at dosing visits. Please check that the required washout period has been met for inhibitor testing, see section 8.1.1.3

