The primary concern in PUPs is the risk of development of inhibitory antibodies to FVIII (inhibitors). Potential development of inhibitors will be monitored by a Nijmegen modified Bethesda assay (which has a high sensitivity for low concentrations of inhibitors), and testing for presence of N8-GP binding antibodies will be performed shortly after each visit. A patient is diagnosed with inhibitor formation if the patient has been tested positive for inhibitors at two consecutive tests from the central laboratory. If antibodies are identified, these will be further characterised on an exploratory basis and there will be close follow-up and case-by-case evaluations.

As with other proteins, allergic type hypersensitivity reactions, including anaphylaxis/anaphylactoid reactions, may occur. As the N8-GP product contains trace amount of hamster cell proteins antibodies to these may occur. Parent(s)/legally acceptable representatives (LAR)(s) to patients enrolled in the present trial will be informed of the signs of immediate type hypersensitivity reactions including hives, pruritus, generalised urticaria, angioedema, hypotension (e.g. dizziness or syncope), shock and acute respiratory distress (e.g. tightness of the chest, wheezing).

PEGylation of proteins is a well-established technology which is used in the treatment of a variety of clinical disorders⁹ and the nonclinical safety profiling of N8-GP has not identified any safety concerns in relation to humans in the dose range proposed for the present trial.

N8-GP is currently being investigated in previously treated patients. The first human dose trial (NN7088-3776) demonstrated that a single dose of N8-GP is generally well-tolerated, and that N8-GP has a prolonged half-life compared to commercially available FVIII products. No safety concerns have been raised based on review of data (cut-off date was 12-Feb-2013) from patients

Protocol v 1 22 of 114

enrolled in the pivotal safety and efficacy trial (NN7088-3859) and the risk/benefit ratio for N8-GP is therefore expected to be favourable.

Protocol v 1 | 23 of 114

UTN: U1111-1148-1897 EudraCT No.: 2013-004025-88 Status: Final Page: 24 of 114

4 **Objective(s) and endpoint(s)**

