For screening failures the screening failure form in the electronic case report form (eCRF) must be completed with the reason for not continuing in the trial. Serious and non-serious adverse events (AE) from screening failures must be transcribed by the investigator into the eCRF. Follow-up of SAEs must be carried out according to Section 11.3. A screening failure session must be made in the IV/WRS. The case book must be signed.

Re-screening is not allowed after the first dose of trial product – see exclusion criterion no. 3 in Section 6.3.

For withdrawn patients

Withdrawn patients are defined as patients who meet the withdrawal criteria after dosing, see Section 6.4

If a patient is withdrawn from the trial, the investigator must aim to perform the End of trial visit, as soon as possible.

The end of trial form must be completed, and final drug accountability must be performed even if the patient is not able to come to the trial site. A withdrawal session must be made in the IV/IWRS and case book must be signed in the eCRF.

All data collected in the period the patient participated in the trial must be documented.

Although a patient or patient's parent(s)/LAR(s) is not obliged to give his/her reason(s) for withdrawing from a trial, the investigator should make a reasonable effort to ascertain the reason(s), while fully respecting the patient's rights. Where the reasons are obtained, the primary reason(s) for discontinuation must be specified on the end of trial form in the eCRF e.g.:

- Adverse events
- Protocol violation
- Lack of efficacy
- Lost to follow up

Protocol v 1 | 42 of 114

- Withdrawal by patient or parent(s)/LAR(s)
- Technical problems
- Other

End of trial

The end of trial (EOT) form should be filled in at the End of trial visit or the last visit of the patient. If a patient is withdrawn prior to completion of the trial, all attempts must be made to schedule the end of trial visit for the patient.

In general

Review of eDiary reports, laboratory reports etc. must be documented either on the front page of the documents and/or in the patient's medical record.

If clarification of entries or discrepancies in the eDiary is needed, the patient's parent(s)/LAR(s) must be questioned and a conclusion made in the medical record. Care must be taken not to bias the patient's parent(s)/LAR(s).

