8.4.3 Blood sampling in infants and children

The blood sampling volume for the patient must not exceed 1% of the total blood volume at one occasion or 3% within in 28 days. This is in accordance with European regulatory guidelines (Directive 2001/20/EC)²².

The total volume of blood to be collected for each patient per visit will not exceed 10 mL.

Detailed instructions will be provided to the trial sites regarding blood sampling volumes and prioritisation of the samples. If trial sites as part of routine assessments perform additional blood draws, they must ensure that the blood sampling volume will not exceed the above requirements.

It is recommended not to attempt venepuncture more than 3 times for the purpose of obtaining sufficient blood sampling. Documentation must be available in medical record.

Port-a-caths and other central venous access devices should preferably not be used for blood sampling due to a risk of dilution or contamination with drugs (e.g. heparin). Should it be necessary to use such a device, it should preferably have been locked with saline prior to use.

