16.3 Primary endpoint

The primary endpoint is a safety endpoint defined as incidence of inhibitory antibodies against FVIII.

The rate of inhibitory antibodies will be reported and a 1-sided 97.5% upper confidence limit will be provided based on an exact calculation for a binomial distribution. For the calculation of the rate the numerator will include the patients with inhibitors, while the denominator will include all patients with a minimum of 10 exposure days plus any patient with less than 10 exposure days but with inhibitors.

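### The primary inhibitor rate counts a patient with 10 or more exposure days as inhibitor-free even if he has no valid central inhibitor test at about his 10th exposure day or later

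*Combined protocol and SAP*

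**What the plan says.** Section 16.3 gives the whole rule for the primary rate. In the numerator, "the numerator will include the patients with inhibitors". In the denominator, "the denominator will include all patients with a minimum of 10 exposure days", together with those who have fewer EDs but an inhibitor. For precision, "a 1-sided 97.5% upper confidence limit will be provided based on an exact calculation for a binomial distribution". Section 3.3 defines a case as a patient who "tested positive for inhibitors at two consecutive tests from the central laboratory".

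No testing condition is attached to the inhibitor-free patients, and there is no rule for missing or invalid tests in this rate. Section 16.4.2.3 reports the high-titre rate in the same way, so it inherits the rule. None of the amendment text supplied changes 16.3. Section 16 allows a separate SAP if one is thought necessary, but none is among the documents.

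On sampling:

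- Table 2–1 schedules an inhibitor test at Visits 1 and 3 and at every visit from Visit 4 on, including EOT.
- Table 2–2, note 9: "Blood samples must be collected prior to dosing at dosing visits".
- Section 8.1, on withdrawn patients: "the investigator must aim to perform the End of trial visit, as soon as possible".
- Section 8.4.3, which limits blood volume and venepuncture attempts in these infants: "Detailed instructions will be provided to the trial sites regarding blood sampling volumes and prioritisation of the samples".

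**The concern.** An exposure-day count shows that a child was at risk. It does not show that the outcome was looked for. A child who passes 10 EDs and leaves without a valid sample from about that time has an unobserved outcome, yet 16.3 enters him as a negative. This is a separate matter from how long patients were exposed.

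The endpoint is a safety rate that will be read against the inhibitor rate of about 30% which Section 11.6.2 expects in this population. For a given number of cases, such patients can move the rate and its upper limit in one direction only, the favourable one. Section 16.4.2.1 accepts that withdrawn patients may differ from completers and adds a sensitivity analysis for the bleeding rate. The primary endpoint has no counterpart.

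**Working it through.** **Plan's own figure.** The only size calculation is in Section 6.5: 100 completers at 20% drop-out need 100/(1 − 0.20) = 125 patients started. This reproduces. No precision is stated for the primary rate.

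**Does the schedule guarantee a test near ED 10?** The windows in Section 8.1.3 are Visit 3 at ED 5 ± 1, Visit 4 at ED 10 ± 2 and Visit 5 at ED 15 ± 2. Because samples are pre-dose, each reflects one ED fewer than the visit's ED number.

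| Visit | ED window | EDs before the sample |
|---|---|---|
| 3 | 4–6 | 3–5 |
| 4 | 8–12 | 7–11 |
| 5 | 13–17 | 12–16 |

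It does not, for these reasons:

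1. A child can have 10 or 11 EDs while Visit 4 is still to come at ED 12. If he leaves then, his last scheduled sample is Visit 3, after at most 5 EDs. Table 2–2, note 2 also lets a visit on prophylaxis stand when bleeds treated at home have pushed actual EDs above the predicted count.
2. A child can have Visit 4 at ED 8 and leave with 10 to 16 EDs before Visit 5. His last scheduled sample then reflects 7 EDs.
3. Visit 4 can take place without a valid sample. Section 8.1.1.3 requires 72 hours of wash-out but exempts some visits from re-scheduling: those for a bleed treated on site during pre-prophylaxis or before home treatment. Pre-prophylaxis can run to ED 20. A sample can also be lost to the blood-volume limit or to failed venepuncture.
4. The EOT sample, which would close the gap, depends on the family returning.

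**Direction.** Let x be the cases, n the patients with a valid test, and m the added patients with 10 or more EDs, no inhibitor found and no such test. The planned rate is x/(n + m). The exact limit is the 0.975 quantile of Beta(x + 1, n + m − x). For fixed x > 0 both fall as m rises. With m = 0 there is no effect.

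**Size.** m is not given. Assume x = 15 and n = 50, in line with the expected 30%.

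| m | Rate | One-sided 97.5% upper limit |
|---|---|---|
| 0 | 15/50 = 30.0% | 44.6% |
| 1 | 15/51 = 29.4% | 43.8% |
| 2 | 15/52 = 28.8% | 43.1% |

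**Why 1 to 2.** Assume that the 20% drop-out is spread evenly over 100 EDs, or 0.2% per ED. The seven EDs from 10 to 16 then hold 7 × 0.2% = 1.4% of patients. That is 0.7 of 50, even if all of them missed EOT. Earlier drop-out or lost samples would raise this somewhat.

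**Cases actually missed.** These children usually have earlier negative tests. If 2 in 50 are affected and the risk remaining after a negative test is assumed to be 5% to 10%, the shortfall is 2 × 0.05/50 = 0.2 points to 2 × 0.10/50 = 0.4 points.

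**The case against.** The strongest reply is that few patients can be affected, and most of it stands:

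- Testing is dense around ED 10, and Section 8.4.2.2 as amended accepts antibody samples within a week of the visit.
- Outside the exempted bleed visits, a visit without wash-out is re-scheduled.
- Section 8.1 also tells sites to make every attempt to hold the EOT visit.
- Section 8.4.2.2 requires an unscheduled visit and a central sample when an inhibitor is suspected, for example because bleeds are hard to treat. Poor responders are therefore not simply lost.
- Section 16 includes patients still in the main phase at the main report only up to their latest visit, so EDs after that visit do not count.
- Nothing in Section 8.4.3 says that the inhibitor sample is the one to be dropped when blood is short.

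A reader might infer that 5 or 10 patients in about 50 would be affected. The documents give no basis for that. Ten added to 50 would be 10/60 = 16.7% of the denominator, close to the whole drop-out assumed through 100 EDs.

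A reader might also infer that the planned rate as a whole is biased down. That is not supported either. The same sentence in 16.3 keeps cases with fewer than 10 EDs but drops inhibitor-free patients with fewer than 10 EDs, which pushes the rate up. Patients confirmed positive before ED 10 remain in the numerator.

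A further objection is that a testing condition removes more negatives while keeping every case. This is fair, and it limits how strict the condition should be. Requiring a sample after at least 10 EDs would reject a Visit 4 held on its nominal day, because a pre-dose sample at ED 10 reflects 9 EDs. Finally, a testing rule in an SAP not supplied cannot be excluded.

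**Conclusion.** The point holds in a limited form. As written, 16.3 scores a patient with 10 or more EDs and no confirmed inhibitor as negative whether or not he has a valid central test at about his 10th ED or later, and the schedule does not guarantee one. For a fixed number of cases, each such patient lowers the rate and its upper limit.

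The effect is probably small: about 0.6 points on the rate and 0.8 on the limit for one patient, or 1.2 and 1.5 points for two. This rests on assumed figures of 15 cases, 50 tested patients and 1 to 2 affected. The conclusion concerns this component only; the net direction of the whole rule is undetermined. The change is worth making because the endpoint is primary, the gap is plain in the text and closing it costs little.

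**What to change.** In 16.3, and by the same rule in 16.4.2.3, define the denominator as:

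- all patients with a confirmed inhibitor, at any ED; plus
- inhibitor-free patients with 10 or more EDs who have at least one valid central inhibitor test (wash-out met) at the scheduled Visit 4, nominal ED 10, or later. EOT and unscheduled samples count.

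Setting the condition at Visit 4 accepts a sample taken anywhere in that visit's window, so it excludes only children with no valid result from about ED 10 onwards. Report how many patients with 10 or more EDs were left out for lack of such a test. Show the rate and limit on the currently planned denominator as a sensitivity analysis, so that the effect of the exclusion is visible.

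The cost is a sentence or two of text, using data already collected. The denominator may be slightly smaller and the rate slightly less favourable.

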16.4 Secondary endpoints

16.4.1 Confirmatory secondary endpoints

There are no confirmatory secondary endpoints in this trial

Protocol v 1 | 93 of 114

Protocol Date: 04 November 2013 Novo Nordisk

 Trial ID: NN7088-3908
 CONFIDENTIAL
 Version: 1.0

 UTN: U1111-1148-1897
 Status: Final

 EudraCT No.: 2013-004025-88
 Page: 94 of 114

16.4.2 Supportive secondary endpoints

16.4.2.1 Number of bleeding episodes during prophylaxis

Annualised bleeding rate will be summarised and a 95% two sided confidence interval will be provided based on a negative binomial regression model with number of bleeding episodes requiring treatment with N8-GP as the outcome variable, and adjusting for exposure time. For comparison with previous trial, a sensitivity analysis based on a Poisson regression model allowing for over-dispersion will also be performed.

Since it must be expected that some patients will withdraw, it becomes essential to account for how such withdrawals may affect the analyses of the prophylaxis effect. The analyses above already account for possible different treatment durations by using treatment duration as an offset. This is a proper adjustment if withdrawal is not related to the observed bleeding frequency. However, since it is possible that patients will withdraw exactly because of the observed bleeding rate it is important to perform sensitivity analyses that may account for withdrawn patients possibly being qualitatively different from completing patients.

Specifically this will be done by performing sensitivity analyses for all prophylaxis analyses using a last observation carried forward (LOCF) approach for all patients with at least 1 month prophylaxis treatment duration by calculating the yearly bleeding episode rate for withdrawn patients and use that as an endpoint. As an example a patient with 6 bleeding episodes in 4 months will have an endpoint value of 18 corresponding to a maintained bleeding rate of 18 bleeding episodes per year. For patients withdrawing within 1 month this method is considered to give too uncertain LOCF values, hence imputation will not be attempted for such patients.

Annualised bleeding rate will also be summarised by type of bleeding episode.

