4.2.2 Secondary Endpoint

- Frequency of Adverse events (AEs) including serious AEs and Medical Events of Special Interest (MESI).*
- Incidence of confirmed high titre inhibitors (defined as inhibitor titre > 5BU)*
- Number of breakthrough bleeding episodes during prophylaxis with N8-GP (annualised bleeding rate).*
- Haemostatic effect of N8-GP in treatment of bleeding episodes, assessed by a predefined 4-point haemostatic response scale ("excellent", "good", "moderate" and "none").*
- Consumption of N8-GP for prophylaxis (number of injections and U/Kg per month and per year)
- Consumption of N8-GP for treatment of bleeding episodes (number of injections and U/Kg required per bleeding episode)
- Total consumption of N8-GP per patient (prevention and treatment of bleeding episodes) per month and annualised value

Protocol v 1 | 24 of 114

^{*}Key supportive secondary endpoint prospectively selected for posting on clinicaltrials.gov

UTN: U1111-1148-1897 EudraCT No.: 2013-004025-88 Version: 1.0
Status: Final
Page: 25 of 114

5 Trial design

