6.5 Patient replacement

Withdrawn patients may be replaced to ensure that 100 patients complete the trial with at least 100 EDs. Assuming a drop-out rate of 20%, it is estimated that 125 patients must be started on N8-GP to obtain the 100 completed patients. This may, however, be adjusted during the trial based on the actual drop-out rate.

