Multiple bleeding locations occurring from the same event (e.g., due to a fall) or at the same time point will be counted as one bleeding episode.

of 114 Protocol v 1 92

Protocol Date: 04 November 2013 Novo Nordisk Version: 1.0

All bleeding endpoints will be evaluated based on bleeding episodes treated with N8-GP unless the bleeding was considered clinically insignificant (non-treatment requiring bleeding episode) and the associated treatment given was part of prophylaxis.

Patients initiating ITI treatment will for the statistical analyses be considered like withdrawals and data collected during ITI treatment period will be summarised and reported separately. Evaluation of these data will be considered exploratory only.

If necessary, a statistical analysis plan (SAP) may be written in addition to the protocol, including a more technical and detailed elaboration of the statistical analyses. If created, the SAP will be finalised before the first database lock.

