16.2 Definition of analysis sets

Descriptions and analysis of efficacy data will be based on the Full Analysis Set (FAS), as defined in ICH E9 guidelines. ²⁶ The FAS includes all patients exposed to N8-GP. The safety analysis and descriptions will be based on the Safety Analysis Set (SAS). The SAS will consist of all patients exposed to N8-GP.

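### The only withdrawal sensitivity analysis for the annualised bleeding rate runs high under the mechanism the plan names, and its gap from the main model does not reliably show which estimate is biased

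*Combined protocol and SAP*

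**What the plan says.** Section 16.4.2.1 estimates ABR from a negative binomial (NB) model of treated bleeds, with treatment duration as offset and a 95% confidence interval. An over-dispersed Poisson model is added for comparison with an earlier trial, not to address withdrawal.

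On the offset the plan says: "This is a proper adjustment if withdrawal is not related to the observed bleeding frequency". It then gives the worry: "it is possible that patients will withdraw exactly because of the observed bleeding rate". The same sentence adds that leavers may differ in kind from completers. The one analysis planned in response works "using a last observation carried forward (LOCF) approach for all patients with at least 1 month prophylaxis treatment duration": the withdrawn patient's own yearly rate becomes his endpoint. In the worked example, 6 bleeds in 4 months become 18, "corresponding to a maintained bleeding rate of 18 bleeding episodes per year". Nothing is imputed for patients who leave within 1 month.

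Two other places bear on this. Section 6.5 gives the planning figure: "Assuming a drop-out rate of 20%, it is estimated that 125 patients must be started on N8-GP". Section 16 counts patients who start ITI as withdrawals, and "data collected during ITI treatment period will be summarised and reported separately". None of the amendments supplied changes Section 16.4.2.1, and Section 16 makes a fuller SAP optional.

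**The concern.** The remedy does not match the stated worry. If a patient leaves because of the bleeds already recorded, the NB model has used that information and LOCF has not: LOCF extrapolates a rate that happened to be high when he stopped. The main model is exposed when withdrawal depends on the patient's underlying rate beyond what his recorded bleeds show.

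A reader who finds LOCF above the main ABR could conclude that the main estimate is too low when it is not, or could dismiss a gap that reflects real bias. The plan gives no rule for reading the gap. It also does not say what value completers receive under LOCF or which model is fitted to the resulting values. What is at stake is the strength of a descriptive statement on bleeding prevention.

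**Working it through.** **1. The plan's own figures.** 6 / (4/12) = 18 per year, as stated. 100 / (1 - 0.20) = 125 starters, as in Section 6.5.

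**2. Exact bias of an own-rate value.** Let a patient bleed at constant rate r and leave at his k-th bleed, at time T. T is gamma distributed with shape k, so E[1/T] = r/(k-1) and E[k/T] = r x k/(k-1). The own rate therefore overstates r on average by 100% at k = 2, 50% at k = 3, 33% at k = 4, 20% at k = 6 and 14% at k = 8.

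**3. Why NB is protected and Poisson is not.** With Y bleeds in time T, a patient contributes r^Y x exp(-rT) x g, where g describes the decision to leave. If g depends only on recorded bleeds, it does not involve r and factors out when r is integrated over its gamma distribution. The NB likelihood is unchanged. If g depends on r, it does not factor out. The Poisson estimate is total bleeds over total time, so it gives frequent bleeders who leave early too little weight.

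**4. Size by simulation.** Inputs from the documents are 20% withdrawn (Section 6.5) and a one-year horizon (100 exposure days at two per week = 50 weeks). Assumed, because the documents give no figures: true ABR 3, dispersion 0.5 to 2, 70 patients, a rate constant over time for each patient, and the exit rules. LOCF is taken as the mean of annualised rates, dropping those who leave within 1 month. There were 300 to 400 trials per setting.

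| Withdrawal | NB | LOCF | Poisson |
|---|---|---|---|
| Constant chance at each bleed | 2.99-3.02 | 3.12-3.26 (+4% to +9%) | 2.38-2.84 |
| Three-monthly review, observed rate above 6/year | 2.98-3.04 | 3.40-3.65 (+13% to +22%) | 2.14-2.73 |
| Half of withdrawals bleed-driven | 2.96-3.02 | 3.06-3.28 (+2% to +9%) | not reported |
| Hazard proportional to underlying rate | 2.66-2.88 (-4% to -11%) | 2.80-2.99 | not reported |

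Coverage of the 95% interval when exit follows observed bleeds is 93-96% for NB. For LOCF it is 91-94% with per-bleed exit and 66-89% with the review rule. When exit follows the underlying rate, NB coverage is 92-94%.

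A separate simulation (30,000 patients per scenario, ABR 1.5 to 6, follow-up of 1 or 2 years) gives the following ratios to the truth. Exit on a high observed rate: NB 0.98-1.01, LOCF 1.05-1.28, Poisson 0.60-0.91. Exit by underlying rate: NB 0.90-0.97, LOCF 0.95-1.00. Exit unrelated to bleeding: all 0.99-1.01. With lognormal instead of gamma rates, observed-bleed exit gives NB 2.91-2.97 and LOCF 3.17-3.57 against a truth of 3.

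**5. Can the gap tell the cases apart?** LOCF minus NB averages 0.13-0.27 with per-bleed exit and 0.09-0.14 with underlying-rate exit. It is positive in 76-94% and 77-87% of trials. A randomly chosen per-bleed gap exceeds a randomly chosen underlying-rate gap with probability 0.52-0.79, where 0.5 is no discrimination.

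**6. Sampling error.** For 70 patients followed one year, ABR 3 and dispersion 1, the variance of a count is 3 + 9 = 12. The standard error is sqrt(12/70) = 0.414, or 0.138 on the log scale. The 95% interval is 3 x exp(+/-1.96 x 0.138), about 2.3 to 3.9.

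**7. What LOCF assumes for the plan's example.** With mean 3 and dispersion 1, the model's expected rate for 6 bleeds in 1/3 year is (1 + 6)/(1/3 + 1/3) = 10.5. Bleeds expected in the remaining 2/3 year are 7, so the model's one-year total is 13. LOCF's 18 implies a rate after withdrawal 18/10.5 = 1.71 times the model's expectation.

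**The case against.** **The plan also has another case in mind.** Its sentence on leavers differing from completers can be read as withdrawal by underlying rate, and there LOCF moves toward the truth. This stands. A reader might infer that LOCF is wrong in every case, and the documents do not support that.

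**A delta grid does not identify the mechanism either.** This stands. Delta = 1 reproduces NB (means within 0.01) and larger deltas exceed it by construction. Delta = 1.5 gives 2.94-3.08 when exit follows the underlying rate. When exit follows observed bleeds it gives 3.26-3.59, and deltas of 2 and 3 give 3.49-5.41, which can lie further above 3 than LOCF does. The gain is that the assumption is explicit, anchored at the main model, and varied.

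**Erring high is conservative in a single-arm summary.** This stands in part: a low LOCF value is reassuring. But LOCF was still slightly low under underlying-rate exit, and dropping early leavers can pull it down. In an extreme setting (39% withdrawn, 9% within a month) the upward bias almost vanished (ratio 1.01).

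**The simulated exits may not describe this trial.** ITI starters count as withdrawals, about 30% of such patients are expected to develop inhibitors (Section 3.1.1), and an inhibitor can change the bleeding rate over time. No mandatory criterion in Section 6.4 is a bleed-rate threshold. This stands as a limit on the sizes. A bleed-driven route does exist, though: Section 5.3.3 requires withdrawal when another FVIII product is chosen because a bleed has not stopped within 48 hours.

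**Part is already handled.** The maintained-rate wording is in the worked example, and ITI-period data are reported separately. What is missing is a statement of when that scenario runs high.

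**Conclusion.** The point holds in limited form. Under withdrawal driven by observed bleeding, the main NB model is approximately unbiased, LOCF is about 4% to 22% high, and Poisson is low. Under withdrawal driven by the underlying rate, NB is about 4% to 11% low and LOCF corrects part of it. LOCF usually lies above NB in both cases, so the gap alone is a poor guide to which estimate is biased, and no planned analysis varies the rate after withdrawal.

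A reader might infer that the gap carries no information. That goes too far: a very large gap points toward exit on a high observed rate, and a small gap shows that the scenario matters little. A reader might also infer that the reported ABR is unreliable. The documents do not support that: the main model is the more robust of the planned analyses under the mechanism the plan names.

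All sizes rest on an assumed ABR, dispersion, exit rules and constant patient rates. The upward direction assumes that high, not low, observed rates prompt withdrawal; this is the natural reading, but the plan does not state it. NB protection assumes the gamma-Poisson model holds at least approximately. Section 16.4.1 has no confirmatory secondary endpoints, ABR has no test or threshold, and the differences are mostly within sampling error. This is a cheap improvement of low priority.

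**What to change.** - Keep the offset NB model on the full analysis set as the main analysis (Section 16.2: "The FAS includes all patients exposed to N8-GP").
- Make the withdrawal sensitivity analysis a multiple imputation from the fitted NB model. With mean rate m and dispersion d, draw the withdrawn patient's rate from a gamma distribution with shape 1/d + Y and rate 1/(d x m) + T. Then draw his remaining bleeds to a pre-specified horizon, for example one year, at delta times that rate, with delta = 1, 1.5, 2 and 3. Redraw the model parameters for each imputation and combine by Rubin's rules. Patients still on prophylaxis at the data cut-off get delta = 1.
- Present the result as a scenario range for the hypothetical rate had prophylaxis continued. It shows how much worse bleeding after withdrawal must be to change the descriptive conclusion. It does not identify the mechanism, is not less biased at every delta, and is not the on-prophylaxis ABR itself.
- Show ITI starters separately from other withdrawals, beside the ITI-period data already planned.
- If LOCF is kept for comparison with earlier trials, label it a maintained-rate scenario that runs high when withdrawal follows observed bleeds. State what completers receive and how the values are modelled.
- Reword the offset sentence. For NB the concern is withdrawal related to the underlying rate beyond the observed bleeds. The Poisson analysis is not protected even when withdrawal follows observed bleeds.

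The cost is SAP wording and modest programming, with no new data and no change to the main analysis. The downside is that results depend on the chosen delta range and horizon.
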